## STUDY PROTOCOL

### A MOBILE PHONE BASED TRIAGE TOOL TO IDENTIFY DISCHARGED TRAUMA PATIENTS IN NEED OF FURTHER CARE IN CAMEROON

#### Protocol Summary

Title	A mobile phone-based triage tool to identify discharged trauma patients in need of further care in Cameroon
Study objectives	
 
1. Establish the feasibility of using mobile phones to follow up on hospitalized trauma patients after discharge in Cameroon.
 
2. Cross-validate a telephone-based triage tool to identify trauma patients who would benefit from further medical care.
 
3. Characterize the impact of timely follow-up on long-term disability and socioeconomic consequences associated with trauma in Cameroon.
 

Study design	
Objective 1: Cohort Study
 
Objective 2: Stepped-wedge intervention, cross-validation of intervention (mHealth telephone triage tool questionnaire) and in-person, blinded physician exam
 
Objective 3: Cohort study

Study sites	
 
1. Laquintinie Hospital of Douala, (Littoral region)
 
2. Limbé Regional Hospital, (Southwest region)
 
3. Pouma Catholic Hospital, (Littoral region)
 
4. Edea Regional Hospital, (Littoral region)
 

Study population	A prospective cohort study of admitted trauma patients in the four-hospital trauma registry
Control arm	Pre-intervention population
Intervention arm	mHealth telephone triage tool implementation
Outcomes	
Aim 1: 1) number and proportion of hospitalized trauma patients who are reached by mobile phone post-discharge.
 
Aim 2: mHealth triage tool score; physician exam determination for “needs further care” or “does not need further care”.
 
Aim 3: Proportion of injured patients who seek clinical follow-up evaluation; GOSE disability level at 2-weeks and at 1, 3, and 6 months

Sample Size	Estimating, that 10% of contacted patients will require further care, a sample size of 1300 patients in the triage cohort will be targeted.
Study duration	24 months

## 1. BACKGROUND

Trauma kills more people annually than HIV, malaria, and tuberculosis combined; 90% of these deaths occur in the developing world. Despite the already-significant burden and the predicted future growth of trauma as a public health problem, trauma remains a non-prioritized public health issue, especially in LMICs. Improvements in trauma care in LMICs could potentially save two million lives each year. As access to adequate care for surgical diseases, like trauma, emerges as a global health priority, innovative methods to improve the quality and efficiency of surgical care are needed.

SSA is disproportionately impacted by injury. Cameroon may be more affected than other countries in the region. While 61% of injured patients are believed to seek formal medical care, there is no mechanism to ensure timely follow up for hospitalized patients. Once patients are discharged from the hospital, their fates are largely unknown. Complications related to injury may not receive further care until conditions are extremely advanced, or they may simply go untreated altogether. Lack of timely intervention for injury-related complications is a potentially preventable cause of morbidity and mortality related to injury.

While mobile phone use in Cameroon is increasing, the sparse literature on their use for health promotion is mainly focused on the use of text-messaging. The feasibility and utility of voice-contact by mobile phone to facilitate of health care services in this context is largely unknown. This growing network of mobile phones presents a potential opportunity to extend health services, even to historically hard-to-reach populations. We propose to use a mobile phone-based triage tool to identify discharged trauma patients who would benefit from further care. Our specific aims are designed to accomplish this objective.

visits.

## 2. STUDY AIMS

The primary study objectives are as follows:

**Aim 1: Establish the feasibility of using mobile phones to follow up on hospitalized trauma patients after discharge in Cameroon.**

*Hypothesis:* Mobile phones are a feasible way of contacting trauma patients after they are discharged from the hospital in Cameroon.

We will contact trauma patients discharged from four hospitals participating in the Cameroon National Trauma Registry at intervals of two weeks, one month, three months, and six months following discharge. The response rate and decay of response over time will be tracked.

**Aim 2: Cross-validate a telephone-based triage tool to identify trauma patients who would benefit from further medical care.**

*Hypothesis:* A triage tool administered over the telephone can effectively identify injured patients who would benefit from further care for their injuries.

An over-the-phone triage tool will be used to predict a binary outcome two-weeks after discharge: needs further care or does not need further care. An independent physician blinded to triage tool outcome who will also render a determination on the same binary outcome, will examine those patients contacted by telephone. Physician assessment will be used as the gold standard to calibrate the model, which will be validated in a separate patient cohort.

**Aim 3: Characterize the impact of timely follow-up on long-term disability and socioeconomic consequences associated with trauma in Cameroon.**

*Hypothesis:* Trauma patients in need of post-hospitalization medical care will have improved disability outcomes if follow-up care is delivered promptly.

Patients will be given a modified Glasgow Outcomes Scale-Extended (GOSE) survey to complete at two weeks, one month, three months, and six months after hospitalization to quantify the death and disability associated with traumatic injury for each patient. Pre- and post-intervention results will be compared.

### **3. METHODOLOGY**

Overall: The study has two linked data collection systems: the trauma registry and the mHealth triage tool. Aims 1, 2, and 3 will run concurrently.

#### **3A. Aim 1**

##### **Study design:**

Aim 1: Prospective Cohort Study

Aim 2: Stepped-wedge intervention, cross-validation of intervention (mHealth triage tool questionnaire) and in-person, blinded physician exam

Aim 3: Cohort study

**Study Population:** The study will be conducted at 4 hospitals (see below) that are part of an existing centralized trauma registry in Cameroon.

1. Laquintinie Hospital of Douala, (Littoral region)
2. Limbé Regional Hospital, (Southwest region)
3. Pouma Catholic Hospital, (Littoral region)
4. Edea Regional Hospital, (Littoral region)

##### **Intervention:** Telephone triage tool

The study will consist of a cohort study (Aim 1), and cross-validation of the triage tool (Aim 2) that will be implemented in a step-wedge fashion to assess preliminary outcomes (Aim 3). Data will be collected using a cell phone follow-up protocol for patients initially presenting for traumatic injury to 4 hospitals in Cameroon: 1) Laquintinie Hospital, a 710-bed governmental public tertiary hospital serving as a national referral center and a local catchment population of over 3,000,000, located in Cameroon's largest urban center; 2) Limbé Regional Referral Hospital, a 170-bed government public hospital serving a mixed urban/rural catchment region of approximately 130,000 people in the Southwest Region of Cameroon; 3) Pouma Catholic Hospital, a 120-bed mission hospital serving a largely rural catchment of 200,000 in the Centre Region of Cameroon; and 4) Edea Regional Referral Hospital. We have an ongoing trauma registry in all 4 facilities. Demographic and clinical data, including cell phone number, are collected on all patients who present to the hospital for injury regardless of severity or disposition. All patients "captured" by the trauma registry who are admitted to the hospital or transferred to an outside hospital for treatment of injury will be included.

**Trauma Registry:** Our collaboration has developed a multi-institutional trauma registry that gathers data on trauma patients presenting to 4 hospitals in diverse contexts: a large, urban tertiary center; a regional referral hospital serving a mixed urban-rural population; and a smaller mission hospital serving a largely rural population. Currently in Cameroon, there is no formal follow-up mechanism for trauma patients discharged from the hospital. Patients return for care when they think there is a problem, often in an extremely delayed fashion that precludes effective intervention.

**Trauma Registry Eligibility:** Patients presenting to the Emergency Department (in four hospitals in Cameroon) with traumatic injury, as defined by the WHO, are approached for inclusion. WHO in its 2004 Injury Surveillance Guidelines defines an injury as "the physical damage that results when a human body is suddenly or briefly subjected to intolerable levels of energy. It can be a bodily lesion resulting from acute exposure to energy in amounts that exceed the threshold of physiological tolerance, or it can be an impairment of function resulting from a lack of one or more vital elements (i.e. air, water, warmth), as in drowning, strangulation or freezing. The time between exposure to the energy and the

appearance of an injury is short. The energy causing an injury may be: mechanical (e.g. an impact with a moving or stationary object, such as a surface, knife or vehicle); radiant (e.g. a blinding light or a shock wave from an explosion); thermal (e.g. air or water that is too hot or too cold); electrical; chemical (e.g. a poison or an intoxicating or mind-altering substance such as alcohol or a drug). Injuries are the acute, physical conditions listed in Chapter XIX (Injury, poisoning, and certain other consequences of external causes) and Chapter XX (External causes of morbidity and mortality) in the International Statistical Classification of Diseases and Related Health Problems, Tenth revision (ICD-10)."

Patients satisfying the following inclusion criteria will be included in the registry:

1. Trauma patients who are formally admitted to the hospital as in-patients.
2. Trauma patients who die upon arriving to the Emergency Departments or while admitted in the hospital.
3. Trauma patients who are transferred to other health facilities.
4. Trauma patients with indications for hospital admission (based on physicians' assessments) but leave against medical advice
5. Trauma patients who are kept under observation in the Emergency Department for over 24 hours.

**Exclusion Criteria:** No patients are excluded based on age, gender, or injury severity. If patients or their surrogate decision-maker do not give consent to participation, those patients will be excluded. According to the WHO definition above, the following will be excluded from the definition of "injury": "Whereas the above definition of an injury includes drowning (lack of oxygen), hypothermia (lack of heat), strangulation (lack of oxygen), decompression sickness or "the bends" (excess nitrogen compounds) and poisonings (by toxic substances), it does NOT include conditions that result from continual stress, such as carpal tunnel syndrome, chronic back pain and poisoning due to infections. Mental disorders and chronic disability, although these may be eventual consequences of physical injury, are also excluded by the above definition." Patients who are not formally admitted and discharged within 24 hours will be excluded.

**Implementation/Data Collection:** The trauma registry data are collected by a single trained research assistant in the emergency department of each hospital under the supervision of a field supervisor. Clinical staff verbally collect information on demographics, injury context, and mechanism from all traumatically injured subjects and/or an adult surrogate. They record this information on a paper trauma registry data collection form. Clinical staff also collect clinical data during patient care.

Each hospital's trained research assistants will then follow up with patients' progress to record complications, outcomes, and final disposition of patients during their time as an inpatient. They will collect trauma registry data collection forms daily from patient's hospital records and managing team and follow the hospital course of each patient that is admitted for further care. By participating in daily rounds, the research assistants will collect information on further treatment and outcomes, including complications and mortality. Research assistants will enter data into the encrypted, password-protected, online database hosted on REDCap ("Research Electronic Data Capture," which is a HIPAA-compliant, secure web application for building and managing online surveys and databases).

**mHealth telephone triage tool:** Our community-based survey found that 95% of respondents had access to a cell phone in their household. Cell phone numbers are also routinely collected as part of the multi-institutional trauma registry's patient demographic data. Pilot data from the 3-site trauma registry suggests that about 57% of urban and 70% of rural households have cellphone access, and 54% of patients overall were willing to provide cell phone numbers for healthcare follow-up after injury. Preliminary testing was done to identify the best method of calling participants that yields the highest response rate. To test the hypothesis that patient-initiated follow-up would vary by time from discharge, we retrospectively identified patients at 3 contact points post-discharge from the hospital (3, 6, and 12 months) and called them during the same 2-week period. During these calls, participants answered the Glasgow Outcomes Score Extended (GOSE) survey. In data collected for 331 patients, 64% of cell phone numbers provided were reached and 39% of subjects or families participated in surveys. Contact rates were slightly higher for patients contacted at 3 months post-discharge (68%) than for those contacted at 6 months (61%) and 1 year (58%), but survey completion rates at all 3 time points were similar. Call outcomes when surveys were not done included failure of the respondent to

know the patient (37%), phone disconnection (29%), and no answer (26%). There were no significant differences in the distribution of non-response by contact time-point.

Several lessons were learned through this preliminary experience. The call testing was done using an account set up through Skype to minimize charges, but this generated an unrecognizable call number viewed by the recipient, potentially deterring them from responding. To mitigate this barrier, we created a dedicated mobile phone account with a recognizable Cameroonian phone number. Additional measures to optimize response rates were also identified based on our local stakeholder feedback: 1) reassurance at the time of data collection that the phone number was not to be used by hospital financial personnel for pursuit of fee collection; 2) initial testing of mobile phone numbers at the time of data collection to ensure that they were accurate; 3) provision of the study cell phone number to patients so the number would be recognizable to them when called; and 4) guarantee of transfer of mobile credits to their phone at the end of each call to reimburse participants for time spent speaking with study staff. These changes will be implemented with the proposed study protocol. Our preliminary study yielded critical information to optimize our proposed study protocol, but response rates when patients are contacted in prospective, longitudinal fashion are unknown; we expect them to increase with implementation of modifications to rectify the challenges identified.

**Triage Tool Development:** Our extensive literature search for existing telephone-based follow-up triage tools for injured patients yielded no directly applicable studies conducted in LMIC settings. A few non-trauma related instruments were developed for HIC and LMIC settings. The one most relevant to our proposed project was a post-operative tool used to follow-up on elective surgery patients in an industrialized country setting. The lack of studies investigating mobile phone follow-up for trauma patients in LMICs led us to review mobile-based follow-up approaches in other fields of medicine and surgery in both HIC and LMIC. Based on this review, we generated a list of potential questions aimed at identifying post-injury individuals in need of further care and modified the questions to reflect relevance to the Cameroonian context. Potential questions were also solicited from local experts, including surgeons and physicians who take care of injured patients in Cameroon. All potential questions from both sources were compiled and reviewed by an expert panel of Cameroonian medical care providers. Redundant questions were combined and refined; ambiguous questions were revised. Any questions found to be non-essential or marginally contributory were removed. The resulting preliminary triage tool consisting of 7 questions (Figure 1) was then pre-tested for acceptability and understandability on a small group of hospitalized patients and family members. In preliminary testing, of 150 triaged patients, 20 (13%) tested as needing further care. The triage tool will be administered via mobile-phone by trained research assistants as described in Aim 2.

Table 1: Questions included in the mobile-phone based triage tool		
#	Question	Answers
1	Is the patient currently alive?	 Yes  No: Date of Death: _____ * Stop interview
2	Since leaving the hospital how have they been feeling?	 Much better  Somewhat better  The same as when I left the hospital  Sicker  Much sicker
3	Have they been able return to usual daily activities?	 Yes  They have returned to some activities, but they are harder and/or require extra help to do them  No
4	Do they need daily help from another person to feed, clothe, bathe, and go to the toilet?	 Yes  No
5	Since leaving the hospital have they had problems...	 Getting food or water?  Taking medicines?  Caring for your injury/wound as instructed?
6	Since leaving the hospital have any of the following things STARTED or GOTTERN WORSE?	 Fever  Redness/Swelling of the injured part  Pain  Difficulty moving or feeling  Drainage or opening of a wound/incision
7	Since leaving the hospital, have they seen another doctor or healer for the injury?	 No  Considered seeking additional treatment  Sought other care but no further treatment given  Received additional treatment

## APPROACH

**Aim 1: Establish the feasibility of using mobile phones to follow up on hospitalized trauma patients after discharge in Cameroon.** This aim will be addressed through a prospective cohort study following discharged trauma patients longitudinally over 6 months. The following data will be extracted from the existing trauma registry: patient demographics, clinical course, injury severity, disposition, and patient cell phone numbers. All admitted trauma patients who provided cell phone numbers in the emergency department will be contacted at intervals of 2 weeks and 1, 3, and 6 months post-discharge. Contact points at 2 weeks and 1 month correspond with traditional post-injury follow-up visits when intervention is theoretically likely to positively impact patient trajectory. These time points have also been used in prior mobile-health follow-up studies in traumatic brain injury and surgical patients in developed settings. Three and 6-month time points were selected because our preliminary data showed higher rates of disability and survey response at 3 and 6 months than at 12 months. Attempts will be made to contact patients at least 3 times by calling and once by text message over a 1-week interval at each time point.

**Outcomes:** number and proportion of successful attempts.

[figure not shown]
**Sample Size:** This overall study is powered for Aim 2 (see below), but the study population for Aim 2 will be used to calculate the number and proportion of successful attempts in Aim 1.

**Data Analysis:** Feasibility will be assessed through calculation of the number of successful contacts; number of attempts required to achieve success; cost associated with personnel and telephone time; reason for contact failure; and survey administration time. Frequencies and proportions of successful contacts will be calculated for each time interval and temporal trends will be described. Mean and standard deviation for personnel time and call cost will be used to calculate average cost per patient contact and determine the overall feasibility of cell phone interviewing as a follow-up method.

**Aim 2: Cross-validate a telephone-based triage tool to identify trauma patients who would benefit from further medical care.**

**Study design:** The 4 hospitals will start in a stepped wedge design the implementation of mHealth telephone triage tool (see Figure 1).

**Implementation/Data Collection:** Patients contacted two weeks after discharge will be asked to give additional consent for participating in the triage tool part of the study. Those who consent will be contacted by research assistants and will answer 7-question survey. Patients whose responses trigger concern about the need for further medical attention will be informed that they should return to care and given appropriate instructions. All patients, regardless of triaged status, will be asked to schedule a time for a physical exam and will undergo one either at the hospital or in their place of residence. If patients return to the hospital, compensation for travel expenses will be provided on a sliding scale. This exam will occur within 1 week of the phone interview. Trained study physicians will conduct a structured, standardized exam that will ultimately culminate in a dichotomous outcome for “needs further care” or “does not need further care”. Based on the exam, the physician will determine if the patient would benefit from further services (including additional follow-up care, diagnostic or therapeutic interventions). Additional data will be collected regarding physician opinion as to whether the patient is demonstrating on-trajectory recovery for their age, health status, and injury, and whether the patient is at high, moderate, or low risk for a poor outcome. At the 2-week and 6-month time points, all contacted patients will be asked about their satisfaction with formal medical services, post-injury follow-up care, perceived convenience, and utility of mobile telephone follow-up.

**Figure 1: Step-wedge design of study.** For each site: Diagonal lines depict a GOSE baseline data collection phase, gray arrows depict intervention phase (1 year/site), and black blocks depict follow-up phase (6 months/site).

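### Aim 1's contact proportion has no single unit or denominator: hospitalized patients reached in the Protocol Summary, successful attempts calculated in the Aim 2 population in the Approach section

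*Combined protocol and SAP*

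**What the plan says.** The Protocol Summary gives the Aim 1 outcome as the "number and proportion of hospitalized trauma patients who are reached by mobile phone post-discharge". It describes the study population as "A prospective cohort study of admitted trauma patients in the four-hospital trauma registry". Section 2 (Study Aims) adds for Aim 1: "The response rate and decay of response over time will be tracked".

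The Approach section describes Aim 1 in other terms. Its opening paragraph says that every admitted patient who left a phone number is to be called at 2 weeks and at 1, 3 and 6 months. Its Outcomes line speaks of successful attempts. Its Sample Size paragraph says the study is powered for Aim 2 and that "the study population for Aim 2 will be used to calculate the number and proportion of successful attempts in Aim 1". Its Data Analysis paragraph says "Frequencies and proportions of successful contacts will be calculated for each time interval and temporal trends will be described" and does not name a denominator.

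Under Aim 2 (Implementation/Data Collection), entry to the triage part follows contact: "Patients contacted two weeks after discharge will be asked to give additional consent for participating in the triage tool part of the study".

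**The concern.** Aim 1 is one of the stated primary objectives. It has no test, threshold or precision target, so the contact proportion at each time point, and its change over time, is the result. A proportion needs a unit and a denominator, and here both differ between sections.

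The Sample Size sentence is the most troublesome. Taken at its word and joined to the Aim 2 entry rule, it points to people who have already been reached at 2 weeks and have agreed to take part. A contact rate calculated in them says nothing about feasibility at 2 weeks. At 1, 3 and 6 months it describes only the more reachable and willing patients. The decline in response that the study sets out to track would then start from an artificial 100%.

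**Working it through.** **The plan's own figure.** The only sample size linked to Aim 1 is the triage cohort (Aim 2, Sample Size). The inputs are 13 variables, 10 participants per variable per outcome, and 10% of contacted patients needing further care. 10 × 13 = 130, and 130 / 0.10 = 1300, which matches the stated target. The 10% is a share of contacted patients, so the 1300 counts people already reached. The plan states no Aim 1 proportion or precision, so there is no Aim 1 figure to reproduce.

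**The definitions side by side.**

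| Place | Unit | Base |
|---|---|---|
| Protocol Summary, Outcomes | patient | hospitalized trauma patients |
| Approach, Aim 1, opening paragraph | patient called | admitted patients who gave a number |
| Approach, Aim 1, Outcomes | attempt | not stated |
| Approach, Aim 1, Sample Size | attempt | Aim 2 study population |
| Approach, Aim 1, Data Analysis | contact | not stated |

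Patient and attempt are not interchangeable: "Attempts will be made to contact patients at least 3 times by calling and once by text message" applies at each time point, so one patient generates several attempts.

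**The literal reading.** Let n be the number of patients contacted at 2 weeks who consented to triage. All n were reached at 2 weeks, so the per-patient proportion is n / n = 100%, whatever the true contact rate. At a later time t the quantity becomes the probability of being reached at t given contact and consent at 2 weeks. That is a different quantity from the proportion of hospitalized patients reached at t.

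**Illustration of the spread.** The inputs come from the pilot results in section 3A (mHealth telephone triage tool): 54% of patients were willing to give a number, and 64% of the numbers given were reached.
- All hospitalized patients: 0.54 × 0.64 = 0.346, about 35%.
- Patients who gave a number: 64%.
- Consented triage cohort: 100% by construction.

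The first line assumes that the two pilot rates can be multiplied. The pilot was retrospective and called patients at 3, 6 and 12 months, not at 2 weeks. Section 3A itself says that prospective response rates are not known. The spread matters here, not any single value.

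**Later time points.** The Addendum says that recruitment of new patients for aGOSE data stopped in June 2021, while the triage tool was given at 2 weeks until August 2022 and the last 2-week follow-up was on September 14, 2022. Patients in the 2-week data may therefore never have been scheduled for the later calls. The Addendum's dates also do not fit together. June 2021 plus 6 months is December 2021, apart from any lag to discharge, but 6-month follow-up is said to have been completed in December 2022 to January 2023, which is 18 to 19 months after the stop.

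**The case against.** A reader might infer that the plan has decided to confine Aim 1 to consented triage patients. The documents do not settle that, and several features point the other way:
- The Protocol Summary and section 3A each give one registry-wide study population, and the plan uses a separate term, triage cohort, for the consented group.
- The sentence sits under Sample Size, where it may say only that Aim 1 was not sized on its own.
- The same section plans to call every admitted patient who gave a number and to record why contact failed. Failures could not occur at 2 weeks among people who had all been reached.

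On the unit, the Data Analysis paragraph lists "number of attempts required to achieve success" separately from contact proportions, so successful attempts may be loose wording for patients successfully contacted. Aim 1 is also descriptive, and the registry and call data would allow any of these denominators to be tabulated.

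Most of this stands. It makes the damaging reading uncertain, but it does not reconcile the sections. Even on the benign reading the Outcomes line counts attempts where the Protocol Summary counts patients, and all hospitalized patients and number-providers both remain possible bases. Being able to tabulate several denominators is not the same as having named one.

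**Conclusion.** The point holds as a conflict of definition in a primary aim. That the sections differ in unit and base is plain from the text. That the analysis would be restricted to the triage cohort is possible but not established. If the sentence were followed literally, the 2-week result would be uninformative and the later ones conditional on earlier contact and consent. The illustrative spread of about 35%, 64% or 100% rests on multiplying the pilot rates and carrying them over to 2 weeks.

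A reader might go further and put figures on success per attempt, on false decay, or on the share of calls made after June 2021. The documents do not support such figures. The number of attempts is given as a minimum, no 2-week contact rate is reported, the pilot did not follow the same patients over time, and recruitment by month is not given. The date discrepancy in the Addendum is secondary: it matters here because it determines who belongs in the later denominators.

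This is not a sample size error. It should be corrected, because it affects the main result of a stated primary objective and the correction is cheap.

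**What to change.** Replace the Sample Size sentence in the Approach section, Aim 1, with:

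> Aim 1 has no separate sample size. The unit is the patient. At each time point the primary proportion is patients reached divided by all admitted registry patients discharged alive whose discharge date placed them in the cohort scheduled for calls at that time point, whether or not they gave a phone number or later declined. Patients without a number and patients who declined stay in the denominator and are shown as separate categories. The secondary proportion uses patients who gave a number. The analysis is not restricted to the triage cohort. Attempts per successful contact are reported separately.

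Use the same definition in the Protocol Summary and in the Aim 1 Outcomes line. Membership is set by discharge date rather than by being due a call, because patients without numbers are never called and, under Informed Consent, households that decline are not contacted again. A rule based on calls due would drop both groups and bring back the conditioning.

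Show post-discharge deaths, and patients whose call window fell in the 2020 suspension, as separate categories. Do not count patients recruited when 1-, 3- and 6-month calls were no longer scheduled as unreached at those points. To set those denominators, reconcile the June 2021 recruitment stop with the December 2022 to January 2023 completion date.

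The cost is rewording in two sections, a check of the Addendum dates and some recoding of call records. The registry supplies the denominator, and attempts and failure reasons are already planned data. The downside is a less favourable feasibility percentage.
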